8. APPENDIX

8.1 Donor variables

Donor Variables	
Biographic Characteristics	Age
	Height
	Weight
	Gender
	Living Donation (1) / Heart beating donation (NDD) (2)/ Non heart beating donor (DCD)
	Cause of Death
	ICU stay

Laboratory values prior to LT and following LT	Sodium Level
	Bilirubin Level
	AST/ALT Level
	Creatinine Levels

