2.1 Liver Transplantation and Model for End-Stage Liver Disease

Liver transplantation (LT) represents an important curative option for end stage liver disease such as decompensated cirrhosis, which remains a major challenge for today's health care system. The Model for End-Stage Liver Disease (MELD) is a worldwide-established scoring system for the evaluation of the severity of liver disease in allocation processes. However, the interpretation of MELD in clinical practice, particularly with regard to prioritizing potential liver transplant recipients, has revealed some hazards. These include the adaptation of MELD based on patient's characteristics, e.g. the presence of hepatocellular carcinoma, kidney failure and cardiovascular disease (Freeman et al. 2002). In addition, the remaining paucity of organ donors contributes to a rising number of transplantations of high MELD recipients. This leads to the risk of impaired outcomes, especially considering the interaction of additional donor and recipient risk factors, such as extended cold preservation, kidney function and warm ischemia (Schlegel et al. 2017). For a certain patient cohort living donation might represent a feasible approach as reported previously for high MELD patients (Selzner et al. 2010). Overall, the interaction of donor and recipient characteristics on the outcomes after LT in high MELD patients remains a scarcely investigated field. Therefore, the identification of factors influencing patient's outcomes after orthotopic liver transplantation becomes increasingly important, especially in high MELD recipients.

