2.2 Aim of the Study

We will create a comprehensive database to address several questions regarding the selection and outcome of liver transplantation in high NaMeld recipients:

1. Is the change of NaMeld score (delta Meld) prior to liver transplantation predictive for post-transplant outcome?
2. What are the characteristics of futile liver transplants in high NaMeld patients (high NaMeld recipients that do well vs early death)
3. Is exceeding the NaMeld threshold of 30 predictive of poor outcome?
4. Do all NaMeld factors are of equal importance for the prediction of futile outcome in high Meld recipients?

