4.2.2. Exclusion Criteria

- Patients undergo transplantation of organ(s) in addition to the liver.
- Patients who are enrolled in clinical trials of other unlicensed therapy.
- Patients younger than 18 years
- Patients for retransplant

5. Data Collection Procedure:

Data from January 01, 2010 to December 31, 2025 will be collected from hospital specific database. The collected data will be identified by unique study identifier only. Data will be stored for ten years after study completion in accordance with requirements of the corresponding ethic committees; publication or data source file stored will not contain any personal identifiers.

6. Data Analyses:

All statistical data will be generated by using JMP 13 (SAS Institute, Cary, NC), SPSS 22 statistical package (IBM, Chicago, IL, USA), or R (The R Foundation for Statistical Computing, Vienna, Austria). The main outcome measure will be the incidence of patient survival among different groups. Cumulative overall rejection-free rates will be calculated by Kaplan-Meier methods and differences between curves will be evaluated with the log-rank test and Bonferroni or Holm's correction. Continuous variable data will be analyzed nonparametrically using the Wilcoxon / Kruskal-Wallis' correction.

Categorical variables will be summarized as counts and proportions and compared by Chi squared test or Fisher's exact test as appropriate. These results will be represented as Odd's ratio or Hazard ratio with 95% confidence interval (CI). $P < 0.05$ will be considered statistically significant.

7. Ethical Consideration:

This protocol was approved by the local ethic committees of participating centers. No study activities will begin until approval is obtained. A waiver of informed consent is requested for this study since it meets the requirements for the common rule. Namely, it would be impractical to attempt to obtain consent for this study since many of these patients may now be deceased and/or lost to follow-up. Further, the exclusion of any patients would impact the quality of the study data. Finally, the study involves minimal risk to participants, as no change to patient care is taking place.

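### Section 6 names only unadjusted tests for a risk-factor aim, so donor type, which is collected, can bias the NaMELD 30 contrast and the donor-factor tests in either direction

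*Protocol*

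**What the plan says.** The synopsis sets the primary objective as finding the main risk factors for long-term survival of high-NaMELD recipients. Section 2.2 adds a threshold question: "Is exceeding the NaMeld threshold of 30 predictive of poor outcome".

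No eligibility criterion concerns the graft source. The exclusions cover multi-organ transplants ("Patients undergo transplantation of organ(s) in addition to the liver"), enrolment in trials of other unlicensed therapy, age under 18, and retransplantation. Section 8.1 lists donor type as a variable to collect: "Living Donation (1) / Heart beating donation (NDD) (2)/ Non heart beating donor (DCD". The same table holds donor cause of death, donor ICU stay, and a block of donor laboratory tests headed "Laboratory values prior to LT and following LT".

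On analysis, section 6 states: "The main outcome measure will be the incidence of patient survival among different groups". For time-to-event data, "differences between curves will be evaluated with the log-rank test and Bonferroni or Holm's correction". For categorical data, "Categorical variables will be summarized as counts and proportions and compared by Chi squared test or Fisher's exact test as appropriate". Continuous data get Wilcoxon or Kruskal-Wallis tests. Results are to be given as odds or hazard ratios with 95% intervals. No stratum, covariate or multivariable model is named anywhere.

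**The concern.** Recipients of living, NDD and DCD grafts all enter the cohort, and NaMELD groups are not randomised. Section 2.1 describes MELD as an allocation tool, names graft-related factors such as cold preservation and warm ischaemia as contributors to poor outcome, and says: "For a certain patient cohort living donation might represent a feasible approach as reported previously for high MELD patients". It is therefore plausible that donor type is related both to NaMELD and to survival. If so, a crude comparison at 30 is partly a comparison of donor mixes.

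The donor factors have a related problem. Cause of death exists only for deceased donors. ICU stay before donation has no counterpart in a living donor. Donor laboratory values after the transplant can come only from living donors. Tested across all donors, such fields can act as markers of donor type.

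At stake are the answer to the threshold question and the list of risk factors the study will report.

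This goes beyond detail left for a SAP. Section 6 chooses the tests, the multiplicity correction and the significance level, and every test it chooses is unadjusted.

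**Working it through.** **Inputs from the protocol.** Three donor types, a threshold of 30, significance at 0.05 (two-sided assumed, since sidedness is not stated), and the tests above. The protocol gives no sample size, number of deaths, power, effect size or donor mix, so there is no figure to reproduce. Everything below rests on assumptions.

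**Step 1: crude ratio from a mixture.** Let s_k be the share of donor type k in a NaMELD group, r_k its hazard ratio against NDD, h the NDD hazard (assumed 0.05 per year) and T the follow-up (assumed 5 years). With no true NaMELD effect, each group's death rate is

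R = Σ s_k(1 − exp(−h r_k T)) / Σ s_k(1 − exp(−h r_k T))/(h r_k),

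and the crude ratio is R(high)/R(low).

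Worked case: living/NDD/DCD shares 35/50/15% in the low group and 15/75/10% in the high group, with r = 0.5, 1, 1.5.
- Five-year death probabilities: 1 − exp(−0.125) = 0.1175, 1 − exp(−0.25) = 0.2212, 1 − exp(−0.375) = 0.3127.
- Low group: 0.1986 deaths over 4.482 person-years = 0.0443 per year.
- High group: 0.2148 over 4.440 = 0.0484 per year.
- Ratio: 1.09, although NaMELD has no effect.

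| Shares living/NDD/DCD, low vs high | r living, DCD | Crude HR, true 1.00 | Crude HR, true 1.25 |
|---|---|---|---|
| 30/60/10 vs 30/60/10 | any tried | 1.00 | 1.25 |
| any tried | 1, 1 | 1.00 | 1.25 |
| 35/50/15 vs 15/75/10 | 0.7, 1.3 | 1.05 | 1.31 |
| 35/50/15 vs 15/75/10 | 0.5, 1.5 | 1.09 | 1.36 |
| 45/40/15 vs 5/93/2 | 0.7, 1.3 | 1.09 | 1.37 |
| 45/40/15 vs 5/93/2 | 0.5, 1.5 | 1.18 | 1.47 |
| 15/70/15 vs 35/60/5 | 0.7, 1.3 | 0.91 | 1.14 |
| 15/70/15 vs 35/60/5 | 0.5, 1.5 | 0.85 | 1.06 |

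The first two rows show that both links are needed for bias. The last two show a real effect partly hidden.

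**Step 2: false-positive rate of the crude log-rank test.** With D deaths and 30% of patients in the high group, z = √(D × 0.30 × 0.70) × ln(HR), and the rejection probability is Φ(z − 1.96) + Φ(−z − 1.96).
- HR 1.05: 6% with 200 deaths, 7% with 400.
- HR 1.18, 200 deaths: z = √42 × 0.1655 = 1.07, giving 19%.
- HR 1.18, 400 deaths: z = √84 × 0.1655 = 1.52, giving 33%.

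**Step 3: simulation with longer follow-up.** No true effect, 25% above 30, censoring uniform over 0 to 16 years, 1,000 datasets per case.
- Living share 30% vs 5%, living HR 0.7: crude HR 1.09, rejection 14%.
- Living share 40% vs 5%, living HR 0.5: crude HR 1.25, rejection 49% (1,500 recipients) or 60% (2,000).
- DCD share 25% vs 5%, DCD HR 1.5: crude HR 0.92, rejection 12%.
- Equal mix: crude HR 1.00, rejection 6%.

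Stratifying by donor type gave HR 1.00 and 5–7% rejection in every case.

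**Step 4: the reverse error, a false donor factor.** Suppose donor type has no effect and high NaMELD has a hazard ratio of 1.5 or 2.0. If 15.5% of living-donor and 39.1% of NDD recipients are in the high group (what the 35/50/15 vs 15/75/10 mix implies when 30% are high), the crude living-vs-NDD ratio is 0.90 or 0.84. With 5% and 50% it is 0.82 or 0.71. With equal shares it is 1.00.

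**The case against.** **Pooling is not stated.** The groups in section 6 are undefined, and donor type could itself be a grouping variable. A promised hazard ratio implies some model, and an unseen SAP could supply strata or covariates. This stands as a limit: a reader might infer that the plan sets out to pool graft types, but the text only fails to name anything that separates them.

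**The background does not establish the link.** A reader might take section 2.1 to mean that living grafts are scarce above 30. It says no such thing. The sentence on living donation concerns its feasibility in high-MELD patients, which could point the other way. Direction and size are unknown.

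**A crude result may be the right answer to a prediction question.** If grafts are assigned partly by NaMELD, donor type may lie on the path from NaMELD to outcome, and stratifying would remove part of the effect. This stands, and is why the crude result should stay.

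**Stratifying everything would harm the risk-factor aim.** With donor type as a stratum, its own hazard ratio cannot be estimated. This also stands and shapes the fix.

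**The donor ICU example depends on coding.** An assumed simulation in which living donors, 25% of the cohort with hazard ratio 0.6, were entered as zero days found a null ICU effect significant in 62% of datasets, against 5% within deceased donors. The protocol does not state that coding. If the field is left blank, living donors drop out and the problem disappears.

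**Donor type is one of several candidates.** Era, aetiology and donor age raise the same issue. That is true, but donor type is already collected and also determines which donor fields have meaning.

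**Conclusion.** The point holds in a limited form. Followed as written, section 6 gives crude contrasts for an observational risk-factor study, and donor type can bias them in either direction if it is related to both NaMELD and survival. Under the assumed inputs a true hazard ratio of 1.00 appears as about 0.85 to 1.25. The mildest non-null case, 1.05, would hardly matter. With either link absent there is no bias. These figures show what could happen and do not estimate what will.

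The documents do not support saying that donor type is known to be tied to NaMELD, that high NaMELD will be made to look harmful rather than safe, or that donor ICU stay will be falsely flagged. Nor should weight be put on the missing numeric code for DCD in section 8.1. It is clerical and may have been lost when the table was extracted.

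**What to change.** In section 6:
- Keep the crude Kaplan-Meier and log-rank result as the answer to the prediction question at NaMELD 30.
- Add a donor-type-adjusted analysis of the same contrast, either a log-rank test stratified by living/NDD/DCD or a Cox model, and show the contrast separately in living-donor and deceased-donor recipients.
- In the risk-factor model, enter donor type as a covariate, not a stratum, so that its own effect can be estimated.
- Analyse donor cause of death and donor ICU stay among deceased donors only.

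In section 8.1, define the donor laboratory values used in the analysis as pre-donation values for all donors.

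No new variable needs collecting for the donor-type adjustment. The cost is a few sentences and a small loss of precision where few recipients above 30 fall in a donor-type group.

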8.2 Recipient Variables

Recipient Variables		
Overall Characteristics	Date of transplant	
	Date of Death	
Biographic Characteristics	Date of Retransplant	
	Date of last clinical visit	
	Age at Transplant	
	Height	
	Weight	
	Gender	
	Etiology of liver Disease	
	Bilirubin; INR; Creatinine; Sodium at MELD	
	Timepoints	
	Creatinine	D1-7
		3 months
		D90
		6months
		yearly
	eGFR	D1-D7
		3 months
		6 months
		yearly
		D90
	INR	6months
		12months
		D7
		3 months
		D90
	AST	6months
		Yearly
		D1 – D7
		3 months
		6months
	ALT	yearly
		D1 – D7
		3 months
		6months
		yearly

	Bilirubin	D7
		3 months
		6months
		yearly
	Sodium	D7
		3 months
		6months
		Yearly
	Alkaline	D7
	phosphatase	3 months
		6months
		Yearly
	Graft Survival at 1, 3, 5, 10 yrs	
Patient Survival at 1, 3, 5, 10 yrs		
Post-transplant ICU Stay		
Readmission within 30 days (1=yes; 0=no)		
Retransplantation date		
Cause of Graft Loss		
Cause of Death		

Freeman, Richard B.; Wiesner, Russell H.; Harper, Ann; McDiarmid, Sue V.; Lake, Jack; Edwards, Erick et al. (2002): The new liver allocation system: moving toward evidence-based transplantation policy. In: Liver Transplantation 8 (9), S. 851–858. DOI: 10.1053/jlts.2002.35927.

Selzner, Markus; Kashfi, Arash; Cattral, Mark S.; Selzner, Nazia; McGilvray, Ian D.; Greig, Paul D. et al. (2010): Live donor liver transplantation in high MELD score recipients. In: Annals of surgery 251 (1), S. 153–157. DOI: 10.1097/SLA.0b013e3181bc9c6a.

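### Dialysis status is not collected at the MELD timepoints, so a creatinine or NaMELD fall caused by dialysis cannot be told from recovery

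*Protocol*

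**What the plan says.** Protocol section 8.2 fixes the recipient data set. Its only entry for the components of the score before transplant is "Bilirubin; INR; Creatinine; Sodium at MELD" timepoints. NaMELD is not listed as a variable of its own, the timepoints are not defined, and neither dialysis nor renal replacement therapy is mentioned anywhere in the protocol.

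Three of the four questions in section 2.2 depend on that entry:

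- Aim 1: "Is the change of NaMeld score (delta Meld) prior to liver transplantation predictive for post-transplant outcome"
- Aim 3: "Is exceeding the NaMeld threshold of 30 predictive of poor outcome"
- Aim 4: "Do all NaMeld factors are of equal importance for the prediction of futile outcome in high Meld recipients"

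The background in section 2.1 is alert to the kidney. Among the difficulties of interpreting MELD it lists adapting the score to patient characteristics, "e.g. the presence of hepatocellular carcinoma, kidney failure and cardiovascular disease". It also names interacting risk factors "such as extended cold preservation, kidney function and warm ischemia".

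The one exclusion in section 4.2.2 that bears on renal patients is "Patients undergo transplantation of organ(s) in addition to the liver". It removes combined liver-kidney recipients. A recipient of a liver alone who is on dialysis stays in the cohort.

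**The concern.** Creatinine and sodium serve in this study as markers of how ill the recipient is. The premise, which is general knowledge and not stated in the protocol, is that dialysis lowers measured creatinine and tends to correct sodium. A recipient whose kidneys fail before transplant may then show better values on exactly the variables listed, although the illness has advanced. With nothing else recorded, that recipient looks the same as one whose kidneys recovered.

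For aim 1, delta MELD could be negative in someone who deteriorated. For aim 3, some recipients could fall into the group at or below 30 for a reason unrelated to milder disease. For aim 4, creatinine and sodium would mix treated and untreated values, which blurs their association with outcome beside bilirubin and INR.

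A statistical analysis plan can specify a score formula, but it cannot use a variable that was never extracted. Section 8.2 is where this protocol settles what is extracted, so the gap belongs to the protocol.

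**Working it through.** The protocol gives no NaMELD formula, sample size or dialysis rate, so it has no figure of its own to reproduce. The check has two parts.

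**1. What the listed data can distinguish.** Take two recipients with the same fall in creatinine and rise in sodium between two MELD timepoints, one through renal recovery and one through dialysis. Every pre-transplant field in section 8.2 can be identical for both. No listed variable separates them, and the section 4.2.2 exclusions remove neither. This step needs no formula.

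For aim 4 it is decisive. The components are compared one by one, so even a total score already adjusted for dialysis would leave the creatinine and sodium values as dialysis left them.

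**2. How far the score could move (illustration only).** The formula and inputs below are assumptions, not taken from the documents.

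- MELD = 3.78 ln(bilirubin) + 11.2 ln(INR) + 9.57 ln(creatinine) + 6.43, with creatinine bounded at 1 to 4 mg/dL.
- NaMELD = MELD + 1.32 (137 − Na) − 0.033 × MELD × (137 − Na), with Na bounded at 125 to 137 and the score capped at 40.
- Before dialysis: creatinine 3.5, sodium 128. On dialysis: sodium 136, measured creatinine 1.2, 1.5, 2.0 or 2.5. Bilirubin and INR held fixed.
- Comparison: creatinine set to 4.0 when dialysed (an assumed scoring rule).

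Worked case, bilirubin 8 and INR 2.0:

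- Before: MELD = 7.86 + 7.76 + 11.99 + 6.43 = 34.04. NaMELD = 34.04 + 1.32 × 9 − 0.033 × 34.04 × 9 = 35.8.
- On dialysis, measured creatinine 2.0: MELD = 7.86 + 7.76 + 6.63 + 6.43 = 28.69 (28.68 from the rounded terms). NaMELD = 28.69 + 1.32 − 0.95 = 29.1, a change of −6.8 from unrounded scores.
- On dialysis, creatinine set to 4.0: NaMELD = 35.5, a change of −0.3.

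| Bilirubin / INR | Before | Dialysed, measured creatinine 1.2 / 1.5 / 2.0 / 2.5 | Range of change | Dialysed, creatinine set to 4.0 |
|---|---|---|---|---|
| 5 / 1.8 | 33.7 | 21.5 / 23.5 / 26.2 / 28.3 | −12.3 to −5.5 | 32.6 |
| 8 / 2.0 | 35.8 | 24.3 / 26.4 / 29.1 / 31.1 | −11.5 to −4.7 | 35.5 |
| 15 / 2.5 | 39.2 | 29.0 / 31.1 / 33.8 / 35.8 | −10.2 to −3.4 | 40 |

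All three profiles start above 30. With measured creatinine, 8 of the 12 cells (4 + 3 + 1) end below 30. With the dialysis value, none does. The count reflects the chosen inputs and estimates nothing about the cohort.

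**Sensitivity to fixed bilirubin and INR.** A creatinine fall from 3.5 to 2.0 costs 9.57 × ln(3.5/2.0) = 5.4 points before the sodium term. An INR rise from 2.0 to 2.0 × exp(5.36/11.2) = 3.2 would cancel it. A worsening patient could therefore show little or no net fall.

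**The case against.** The strongest reply is that the protocol never says the score is computed from measured creatinine. It gives no formula, and the hospital database from which the data come might hold a score already adjusted for dialysis. Section 2.1 speaks of adapting MELD to characteristics that include kidney failure, which weighs somewhat against assuming an unadapted score. If the intended NaMELD version has a dialysis rule, scoring it as defined would apply that rule, and score derivation is commonly left to the analysis plan.

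Much of this stands. A reader might infer that NaMELD is built from raw values and that the sickest recipients are misclassified. The documents do not support that as fact. Nor can one say that many recipients cross 30: the coefficients and inputs are assumed, some scenarios stay above 30, bilirubin or INR may rise and offset the fall, and the number dialysed is unknown. A recipient dialysed at every MELD timepoint shows no dialysis-driven change in delta MELD at all.

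What does not stand is the step from there to no finding. No stored score is listed for collection and the four laboratory values are, so deriving the score from them is the natural reading. A scoring rule for dialysed patients cannot be applied without knowing who is dialysed. An adjusted total does not help aim 4.

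A similar concern could be raised about the creatinine and eGFR values after transplant. These are secondary laboratory measures, and ranking dialysed recipients as a separate worst category would be an analyst's preference, not the correction of an error.

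**Conclusion.** The point holds as a conditional one. Section 8.2 omits dialysis status at the MELD timepoints, and from the listed data a dialysis-driven fall in creatinine or correction of sodium cannot be told from recovery. If measured values are used, delta MELD may be falsely negative (aim 1) and some recipients may be placed below 30 (aim 3). The blurring of creatinine and sodium in aim 4 does not depend on the score version. All three effects rest on the premise that dialysis shifts the measured values and on liver-alone recipients who were dialysed being present in the cohort.

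The size cannot be derived from the documents. The illustrative falls show only that the shift can be large enough to matter for a cut at 30. The material does not establish a bias of known direction or size in the study's results. This is a cheap improvement to the data set, not a demonstrated error in the analysis.

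**What to change.** - Add to section 8.2 a renal replacement therapy item (yes/no, with date) at each pre-transplant MELD timepoint.
- State which NaMELD version is used and apply that version's handling of dialysed patients when computing the score and its change.
- In aim 4, enter dialysis status beside creatinine.
- Report aims 1 and 3 with a sensitivity analysis by dialysis status. This also shows how many recipients are affected, which the present list would not allow.
- Optional: record dialysis at the postoperative creatinine and eGFR timepoints, so that those values can be shown by dialysis status.

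The cost is one or two extra chart items per patient from the same hospital database and a line in the score derivation. Adding the item before extraction avoids a second pass through the records. No change to patient care is involved.

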1. SYNOPSIS

Study Title	Elucidating major impact factors for high MELD recipient outcomes after orthotopic liver transplantation in adults.
Trial Design	Retrospective cohort study.
Trial Participants	High MELD patients receiving a liver transplant.
Planned Sample Size and Trial Duration	Eligible patients that received a liver graft within the last 15 years.
Trial duration	Up to 15 years Follow up.
Data Collection Period	January 01, 2010 to December 31, 2025
Primary Objective	To identify main risk factors for long term survival of high Sodium medical Model for End-Stage Liver Disease (NaMELD) patients and long-term graft survival after liver transplantation, with the aim prevent and treat pivotal factors prior to transplantation.
Secondary Objectives	
To confirm the risk factors for other long and short-term complication in high NaMELD patients.
 
To investigate the combination of risk factors and NaMELD graduation over time.

Primary Endpoint	Patient survival after liver transplantation.
Secondary Endpoints	
Assessment of biochemical parameters of liver function in the recipient during the initial postoperative phase and during the Follow up.
 
ICU stay.
 
Reasons for graft loss, death and retransplantation.

2. BACKGROUND AND RATIONALE:

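### Section 6 assigns no censoring-aware method to patient or graft survival, so 5- and 10-year survival will be biased if the milestone items in Appendix 8.2 are tabulated as proportions

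*Protocol*

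**What the plan says.** Appendix 8.2 of the protocol lists "Patient Survival at 1, 3, 5, 10 yrs" and "Graft Survival at 1, 3, 5, 10 yrs" among the recipient variables. The same table lists the dates of transplant, death, retransplantation and last clinical visit.

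The synopsis gives the cohort as "Eligible patients that received a liver graft within the last 15 years", with "Up to 15 years Follow up". Section 5 states: "Data from January 01, 2010 to December 31, 2025 will be collected from hospital specific database". Nowhere is there an earlier last transplant date, a minimum follow-up, or a rule for a recipient who has not reached a milestone.

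Section 6 says: "The main outcome measure will be the incidence of patient survival among different groups". The next sentence reads: "Cumulative overall rejection-free rates will be calculated by Kaplan-Meier methods and differences between curves will be evaluated with the log-rank test". Then: "Categorical variables will be summarized as counts and proportions and compared by Chi squared test" or Fisher's exact test. Odds ratios and hazard ratios are both named, and neither is assigned to an endpoint.

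**The concern.** Patient survival is the primary endpoint, and the synopsis puts long-term graft survival into the primary objective. Yet the only censoring-aware method in section 6 is tied to rejection-free rates, and Appendix 8.2 lists no rejection variable. What section 6 offers for a yes/no status is a proportion and a Chi squared test.

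That route handles recent transplants badly. Take two recipients transplanted on the same day in 2022. If one dies in 2023, that recipient's 10-year status is settled: dead. The other, alive at the end of 2025, has no 10-year status. Whether the item can be filled depends on the outcome. Tabulating the filled items keeps recent deaths and drops recent survivors, so survival is understated. Counting recent survivors as having survived errs the other way.

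The error grows with the share of recent transplants. Section 2.1 speaks of a rising number of transplants in high MELD recipients, so the groups to be compared may differ in follow-up. Groups with equal true survival could then appear to differ.

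**Working it through.** The protocol gives no survival rate, event count or sample size, so there is no figure of its own to reproduce.

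**Inputs from the protocol:** milestones t of 1, 3, 5 and 10 years (Appendix 8.2); a data window of T = 16 calendar years (section 5); significance level 0.05 (section 6).

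**Assumptions:** transplants spread evenly over the window, constant hazard h, and complete follow-up to the cut-off. I use h = 5% per year, with 3% and 8% as a range.

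**Step 1. Share who cannot have reached t by the cut-off:** t/16, that is 6.25%, 18.75%, 31.25% and 62.5% at 1, 3, 5 and 10 years.

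**Step 2. Survival among recipients of known status.**

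- P = (16 − t)/16, the share with enough potential follow-up.
- S = exp(−ht), true survival.
- D = [t − (1 − S)/h]/16, the share short of the milestone who have already died.
- Known-status survival = P·S/(P + D).
- If recent survivors are coded as survived, the figure is 1 − [P(1 − S) + D].

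At t = 10 and h = 0.05: P = 0.375, S = 0.607, P·S = 0.2274 and D = (10 − 7.869)/16 = 0.1332. Known-status survival is 0.2274/0.5082 = 0.448. The opposite coding gives 1 − (0.1475 + 0.1332) = 0.719.

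At t = 5: P = 0.6875, S = 0.779, P·S = 0.5354 and D = (5 − 4.424)/16 = 0.0360. Known-status survival is 0.5354/0.7235 = 0.740. The opposite coding gives 0.812.

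| Milestone | True | Known status only | Difference |
|---|---|---|---|
| 1 year | 0.951 | 0.950 | −0.001 |
| 3 years | 0.861 | 0.847 | −0.014 |
| 5 years | 0.779 | 0.740 | −0.039 |
| 10 years | 0.607 | 0.448 | −0.159 |

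At 10 years, hazards of 3% and 8% give 0.604 against 0.741 true and 0.296 against 0.449 true. With a 15-year window, as in the synopsis, the 5% case gives 0.425 instead of 0.448.

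**Step 3. Group comparison.** Simulation of 4,000 datasets with 300 per group (an assumed size), the same 5% hazard in both groups and uniform accrual in one of them. The Chi squared test is applied to known status:

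| Accrual in the other group | Rejects at 5 years | Rejects at 10 years |
|---|---|---|
| Uniform | 5.0% | 5.0% |
| Rate doubles over the window | 6.3% | 8.8% |
| Rate triples over the window | 6.8% | 16.5% |
| Rises linearly from zero | 16.5% | 71% |

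A repeat of the last row gave 14.7% and 70.5%.

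**Step 4. Does time-to-event analysis cure it?** In a further simulation one group's accrual rose from zero while the other's fell to zero, with 100 or 200 per group and true 5-year survival of 0.6 to 0.8. The Chi squared test rejected in 16% to 35% of datasets at 5 years and 51% to 86% at 10 years. The log-rank test on the dates rejected in 4.6% to 6.3%.

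**Step 5. Would restricting each milestone to recipients transplanted early enough suffice?** Only with complete follow-up. With a loss rate l, known-status survival among those recipients is A/(A + B), where A = exp(−10(h + l)) and B = [h/(h + l)](1 − A). For h = 0.05 and l = 0.02, 0.497/(0.497 + 0.360) = 0.58. For l = 0.05, 0.368/(0.368 + 0.316) = 0.54. True survival is 0.61. The loss rates are assumed, but section 7 of the protocol itself expects patients lost to follow-up.

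**The case against.** The strongest reply is that the protocol does not commit to the biased analysis. Appendix 8.2 holds every date a censored analysis needs. It gives no coding for the survival lines, although it does code readmission as yes/no, so those lines may name rates to be derived from the dates. Section 6 never calls milestone survival categorical, and it does name Kaplan-Meier, log-rank and hazard ratios directly after the main outcome. Rejection-free may simply be a drafting slip for survival. Permitted values and missing-data rules normally belong in a data dictionary or SAP.

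Much of this stands. A reader might infer that survival is recorded only as milestone status, or that a Chi squared test on it is prescribed. The documents support neither: the first is contradicted by the listed dates, and the second is an inference from the general rule for categorical variables. The absence of a value for milestones not yet reached is therefore not an error in itself.

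A reader might also take 71% as the expected false-positive rate. It is not. It needs accrual rising from zero in one group and flat in the other, whereas section 2.1 makes only a general remark with no figure for this centre. With equal accrual the test holds its level.

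What the reply does not remove is that section 6, as worded, gives the primary endpoint no censoring-aware method and leaves the proportion route open. This is a matter of what the protocol states, not of detail left to a SAP.

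**Conclusion.** The concern holds as a conditional one. If the milestone items are tabulated under the rule for categorical variables, long-term survival is misstated: by about 4 percentage points at 5 years and 16 at 10 years under a 5% yearly hazard, uniform entry over 16 years and no other loss. At 10 years the understatement is about 14 to 16 points for hazards of 3% to 8%. At 1 year it is negligible and at 3 years small.

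False differences between groups require transplant dates to differ between them. The 10-year rejection rate then runs from nominal, through about 9% when one group's accrual doubles, to about 71% in the extreme case, with an assumed 300 per group. The direction of the bias follows from the structure of the data. Its size rests on the assumed hazard and accrual, which the protocol does not give.

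The point deserves correction because it touches the primary endpoint and the remedy is cheap.

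**What to change.** In section 6, state that patient and graft survival are analysed as time to event from transplant, using the dates already listed in Appendix 8.2, with one stated rule for censoring at last visit or data cut-off. Say which dates define graft loss: the appendix lists a cause of graft loss, but event dates only for retransplantation and death. Read the 1-, 3-, 5- and 10-year values from Kaplan-Meier curves with numbers at risk, compare groups by log-rank test or hazard ratio, and state that the Chi squared rule does not apply to milestone status.

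Adding a not-yet-reached category and limiting each milestone's denominator by transplant date is not an adequate substitute, because it stays biased once patients are lost to follow-up (step 5 of the working).

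The cost is one or two sentences and no new data. Intervals at 10 years will be wide, since under uniform entry only 37.5% of recipients have 10 years of potential follow-up. That reflects the information actually available.
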